13.2. Data Retention

The Principal Investigator (PI) or his/her designee or Investigational site will maintain all essential study documents and source documentation that support the data collected on the study subjects in compliance with applicable regulatory requirements.

The PI or his/her designee will take measures to prevent accidental or premature destruction of these documents. If for any reason the PI or his/her designee withdraws responsibility for

	Form/Template 92120219_Rev/Ver D		
Confidential	LUX-Dx PERFORM Protocol, 92557593, Rev/Ver C		
	Page 42 of 66		
maintaining these essential documents, custody must be transferred to an individual who will			
assume responsibility and BSC must n	receive written notification of this custodial change.		
Sites are required to inform Boston Scientific in writing where paper or electronic files are			

maintained in case files are stored off site and are not readily available.

13.3. Technical Source Forms (TSF)

A TSF is developed by BSC or by the investigational site to capture protocol required data elements that are not duplicated in any other source documents. This form is to be used by the study sites as a source document. A BSC representative may complete the TSF at the request of the Principal Investigator. The TSF will be reviewed and signed for approval by the Principal Investigator or his/her designee at the end of each procedure.

13.4. Core Laboratories

Independent Core lab(s) will be used to provide the extended Holter monitoring product, service, and data analysis. Separate instruction on working with the Core lab and applicable training will be provided.

14. Deviations

An Investigator must not make any changes or deviate from this protocol, except to protect the life and physical well-being of a subject in an emergency. An investigator shall notify the sponsor, the reviewing IRB/EC, and the regulatory authority, if applicable of any deviation from the investigational plan to protect the life or physical well-being of a subject in an emergency, and those deviations which affect the scientific integrity of the clinical investigation. Such notice shall be given as soon as possible, but no later than 5 working days after the emergency occurred, or per prevailing local requirements, if sooner than 5 working days.

All deviations from the investigational plan, with the reason for the deviation and the date of occurrence, must be documented and reported to the sponsor using the relevant CRF. Sites may also be required to report deviations to the IRB/EC, and the regulatory authority, per local guidelines and national/government regulations.

Deviations will be reviewed and evaluated on an ongoing basis and, as necessary, appropriate corrective and preventive actions (including IRB/EC/Regulatory Authority notification, site re-training, or site discontinuation/termination) will be put into place by the sponsor.

The sponsor will not approve protocol waivers.

15. Device Accountability

The devices and equipment used in this study will be commercially approved in all geographies where the study is being conducted. Any device tracking and accountability will occur per the required local regulations for commercial devices.

92557593 C.3 Page 42 of 66

Form/Template 92120219_Rev/Ver D LUX-Dx PERFORM Protocol, 92557593, Rev/Ver C Page 43 of 66

16. Compliance

16.1. Statement of Compliance

This clinical investigation is financed by the study sponsor. Before the investigational site can be "Authorized to Enroll," the investigational site must enter into a Clinical Study Agreement with the sponsor that details the financing of the study as well as the rights and obligations of the investigational site and the investigator. This study will be conducted in accordance with post market clinical follow-up guidelines and will follow the applicable sections of ISO 14155 (Clinical Investigation of Medical Devices for Human Subjects – Good Clinical Practice), the relevant parts of the ICH Guidelines for Good Clinical Practices, ethical principles that have their origins in the Declaration of Helsinki, and applicable individual country laws and regulations. The study shall not begin until the required approval/favorable opinion from the IRB/EC and/or regulatory authority has been obtained, if appropriate. Also, the study shall not begin prior to issuance of the site ATE, as provided by the sponsor. Any additional requirements imposed by the IRB/EC or regulatory authority shall be followed, if appropriate.

16.2. Investigator Responsibilities

The PI of an investigational site is responsible for ensuring that the study is conducted in accordance with the Clinical Study Agreement, the Clinical Investigation Plan, the spirit of ISO 14155, ethical principles that have their origins in the Declaration of Helsinki, any conditions of approval imposed by the reviewing IRB/EC, and prevailing local and/or country laws and/or regulations, whichever affords the greater protection to the subject.

The PI's responsibilities include, but are not limited to, the following:

- Prior to beginning the study, sign the Clinical Study Agreement and comply with the Investigator responsibilities as described in such Agreement.
- Provide his/her qualifications and experience to assume responsibility for the proper conduct of the study and that of key members of the site team through up-to-date curriculum vitae or other relevant documentation and disclose potential conflicts of interest, including financial, that may interfere with the conduct of the clinical study or interpretation of results.
- Make no changes in or deviate from this protocol, except to protect the life and physical well-being of a subject in an emergency; document and explain any deviation from the approved protocol that occurred during the course of the clinical investigation.
- Maintain source documents throughout the clinical study and ensure their availability with direct access during monitoring visits or audits; ensure that all clinical-investigation-related records are retained per requirements.
- Ensure that data reported to the sponsor in the CRFs and in all required reports are attributable, legible, timely, original, accurate, and complete.

- Record, report, and assess (seriousness and relationship to the device/procedure) every adverse event as applicable per the protocol and observed device deficiency.
- Report to sponsor, per the protocol requirements, all reportable events.
- Report to the IRB/EC and regulatory authorities any SAEs and device deficiencies that could have led to a SADE and potential/USADE or UADE, if required by applicable laws or regulations or this protocol or by the IRB/EC, and supply BSC with any additional requested information related to the safety reporting of a particular event.
- Maintain records and control of the device, ensuring that the study device is used only by authorized/designated users and in accordance with this protocol and Instructions For Use.
- Allow the sponsor to perform monitoring and auditing activities, and be accessible to the clinical research monitor or auditor and respond to questions during monitoring visits or audit(s).
- Allow and support regulatory authorities and the IRB/EC when performing auditing activities.
- Ensure that informed consent is obtained and documented in accordance with applicable laws, this protocol and local IRB/EC requirements.
- Provide adequate medical care to a subject during and after a subject's participation in a clinical study in the case of adverse events, as described in the ICF.
- Inform the subject of the nature and possible cause of any adverse events experienced.
- As applicable, provide the subject with necessary instructions on proper use, handling, storage, and return of the device when it is used/operated by the subject.
- Inform the subject of any new significant findings occurring during the clinical investigation, including the need for additional medical care that may be required.
- Provide the subject with well-defined procedures for possible emergency situations related to the clinical study, and make the necessary arrangements for emergency treatment, as needed.
- Ensure that clinical medical records are clearly marked to indicate that the subject is enrolled in this clinical study.
- Ensure that, if appropriate, subjects enrolled in the clinical investigation are provided with some means of showing their participation in the clinical investigation, together with identification and compliance information for concomitant treatment measures (contact address and telephone numbers shall be provided).
- Inform, with the subject's approval or when required by national regulations, the subject's personal physician about the subject's participation in the clinical investigation.

- Make all reasonable efforts to ascertain the reason(s) for a subject's premature withdrawal from clinical investigation while fully respecting the subject's rights.
- Ensure that an adequate investigation site team and facilities exist and are maintained and documented during the clinical investigation.

All investigators will provide their qualifications and experience to assume responsibility for their delegated tasks through up-to-date curriculum vitae or other relevant documentation and disclose potential conflicts of interest, including financial, that may interfere with the conduct of the clinical study or interpretation of results.

16.2.1. Delegation of Responsibility

When specific tasks are delegated by an investigator, including but not limited to conducting the informed consent process, the PI is responsible for providing appropriate training to ensure study staff are competent to perform the tasks they have been delegated. Adequate supervision of the study staff by an investigator is required. Where there is a sub-investigator at a site, the sub-investigator should not be delegated the primary supervisory responsibility for the site. The PI is accountable for regulatory violations resulting from failure to adequately supervise the conduct of the clinical study.

16.3. Institutional Review Board

The investigational site will obtain the written and dated approval/favorable opinion of the Institutional Review Board (IRB)/Ethics Committee (EC) for the clinical investigation before recruiting subjects and implementing all subsequent amendments.

A copy of the written IRB/EC approval of the protocol (or permission to conduct the study) and ICF, must be received by the sponsor before recruitment of subjects into the study. Prior approval must also be obtained for other materials related to subject recruitment or which will be provided to the subject.

Any amendment to the protocol will require review and approval by the IRB/EC before the changes are implemented to the study. All changes to the ICF will be BSC and IRB/EC approved; a determination will be made regarding whether a new ICF needs to be obtained from participants who provided consent, using a previously approved ICF.

Annual IRB/EC approval and renewals will be obtained throughout the duration of the study as required by applicable local/country laws or regulations or IRB/EC requirements. Copies of the study reports and the IRB/EC continuance of approval must be provided to the sponsor.

16.4. Sponsor Responsibilities

All information and data sent to BSC concerning subjects or their participation in this study will be considered confidential by BSC and will be kept confidential in accordance with all applicable laws and regulations. Only authorized BSC personnel and/or a BSC representative including, but not limited to Contract Research Organization (CRO), will have access to this information. Authorized regulatory personnel have the right to inspect and copy all records pertinent to this study. Study data collected during this study may be used by BSC for the

purposes of this study, publication, and to support future research and/or other business purposes, such as overseeing and improving the performance of its device, new medical research and proposals for developing new medical products and procedures. All data used in the analysis and reporting of this study or shared with a third-party researcher will be without identifiable reference to specific subjects.

Information received during the study will not be used to market to subjects. Subject names will not be placed on any mailing lists or sold to anyone for marketing purposes.

16.4.1. Role of Boston Scientific Representatives

BSC personnel can provide technical support to the investigator and other health care personnel (collectively HCP) as needed during implant, testing required by the protocol, and follow-ups. Support may include HCP training, addressing HCP questions, or providing clarifications to HCPs concerning the operation of BSC equipment/devices.

At the request of the investigator and while under investigator supervision, BSC personnel may operate equipment during implant or follow-up, assist with the conduct of testing specified in the protocol, and interact with the subject to accomplish requested activities.

BSC personnel may perform certain activities to ensure study quality. These activities may include the following:

- Observing testing or medical procedures to provide information relevant to protocol compliance
- Reviewing collected data and study documentation for completeness and accuracy

Boston Scientific personnel will not do the following.

- Practice medicine
- Provide medical diagnosis or treatment to subjects
- Discuss a subject's condition or treatment with a subject
- Independently collect critical study data
- Enter data in electronic data capture systems or on paper case report forms

16.5. Insurance

Where required by local/country regulation, proof and type of insurance coverage, by BSC for subjects in the study will be obtained.

17. Monitoring

Monitoring will be performed during the study to assess continued compliance with the protocol and applicable regulations. In addition, the clinical research monitor verifies that study records are adequately maintained, that data are reported in a satisfactory manner with respect to timeliness, adequacy, and accuracy, and that the PI continues to have sufficient staff and facilities to conduct the study safely and effectively. The Principal

Form/Template 92120219_Rev/Ver D Confidential LUX-Dx PERFORM Protocol, 92557593, Rev/Ver C Page 47 of 66 estigator/institution guarantees direct access to original source documents by BSC

Investigator/institution guarantees direct access to original source documents by BSC personnel, their designees, and appropriate regulatory authorities.

The sponsor will put a plan in place to document the specific monitoring requirements.

The study may also be subject to a quality assurance audit by BSC or its designees, as well as inspection by appropriate regulatory authorities. It is important that the PI and relevant study personnel are available during on-site or remote monitoring visits or audits and that sufficient time is devoted to the process.

18. Potential Risks and Benefits

18.1. Risks Associated with Participation in the Clinical Study

This study will enroll patients who are already indicated to receive an ICM per standard of care and meet the study's eligibility criteria. It involves the collection of data via CRF completion and via LATITUDE Clarity, as well as related clinical event data. There are no specific required treatments or therapeutic interventions in this study. There are no other, additional risks of participating beyond what would be expected with standard of care.

A subgroup of subjects (~600) will wear an extended Holter monitor as required by this study. This device is commercially approved in the US and, despite not being mandatory for patients who receive an ICM, is part of the tools available for clinicians to support medical diagnosis and treatment.

18.2. *Risks Related to the Systems Used in the Study according to their Instructions For Use Manuals*

18.2.1 Extended Holter monitor (anticipated adverse events associated with the use of adhesive patches)

• Minor discomfort, skin irritation, reddening, itching, or rash.

18.2.2 LUX-Dx ICM system (anticipated adverse events associated with the implantation of the LUX-Dx ICM)

- Device migration
- Erosion
- Foreign body rejection phenomena
- Formation of hematomas or seromas
- Infection
- Local tissue reaction
- Tissue damage

Refer to the currently available LUX-Dx ICM User's Manual for an updated list of potential adverse events.

18.3. Possible Interaction	ons with Concomitant Medical Treatments, if applicable
	Page 48 of 66
Confidential	LUX-Dx PERFORM Protocol, 92557593, Rev/Ver C
	Form/Template 92120219_Rev/Ver D

There are no concomitant medical treatments.

18.4. Risk Minimization Actions

Additional risks may exist. Risks can be minimized through compliance with this protocol, performing procedures in the appropriate hospital environment, adherence to subject selection criteria, close monitoring of the subject's physiologic status during research procedures and/or follow-ups, and by promptly supplying BSC with all pertinent information required by this protocol.

18.5. Anticipated Benefits

Subject who participates in the Holter study may receive additional arrhythmia monitoring in the 14-day monitoring period by wearing the Holter monitor.

There may be no additional benefit to the subject. However, medical science and future patients may benefit from their participation in this post-market study.

18.6. Risk to Benefit Rationale, if Applicable

The implantable device systems and accessories used for this clinical study will be commercially available and are considered to be standard of care for patients indicated for the LUX-Dx ICM implants. The risks involved with subject participation in this study are essentially the same as those to the patients not participating in the study.

19. Safety Reporting

19.1. Reportable Events by Study Site to Boston Scientific

It is the responsibility of the investigator to assess and report to BSC any event which occurs in any of the following categories:

- Serious Adverse Events
- Serious Adverse Device Effects
- Device Related Adverse Events
- Study Procedure Related Adverse Events
- Cardiac Related Adverse Events
- ICM Related Device Deficiencies
- Unanticipated Adverse Device Effects
- Unanticipated Serious Adverse Device Effects
- New findings/updates in relation to already reported events

When possible, the medical diagnosis should be reported as the Event Term instead of individual symptoms.

If it is unclear whether an event fits one of the above categories, or if the event cannot be isolated from the device or procedure, it should be submitted as an adverse event and/or device deficiency.

Any reportable events, experienced by the study subject after informed consent, whether prior to, during, or subsequent to the implant procedure, must be recorded on the CRF.

Underlying diseases and chronic conditions are not reported as AEs unless there is an increase in severity or frequency during the course of the investigation. Death should not be recorded as an AE, but should only be reflected as an outcome of one (1) specific SAE (see Table 19-1 for AE definitions).

Refer to Instructions For Use for the known risks associated with the commercial device(s).

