Data Collection	Retention of Original Source Documentation
Information regarding the extended Holter monitor distribution, return, and data download and transmission	Study Site
Downloaded Holter monitor device raw data	Core lab and BSC
Extended Holter monitoring report and ECG strips	Core lab; a report copy is sent to BSC and Study Site
Reportable adverse events (as defined in Section 19.1) and protocol deviations, if applicable	Study Site

Table 10-5: 2-Month Holter Visit Source Documentation

10.8. 6-Month and 12-Month EMR Review (±30 days)

A review of each implanted subject's EMR must be performed at 6 months (\pm 30 days) and 12 months (\pm 30 days) post-ICM implant. Subjects are not required to visit the study site in-person. Reportable adverse events defined in Section 19.1 shall be collected. To supplement the EMR review, a phone call or virtual health visit to the subject must be attempted and documented to obtain adverse event information that may not be recorded in the EMR. If the subject is seen in-office that might be part of the standard-of care, then a phone call/virtual health visit is not required. It is not a study deviation if the subject cannot be reached by phone or virtual health visit despite attempts. In addition, any ICM reprogramming (to be documented throughout the study duration), arrhythmia diagnoses facilitated by the ICM, and the resulting arrhythmia treatments will be collected on the appropriate CRF. Site staff will confirm successful LATITUDE Clarity device transmission within the last 90 days to determine if the subject may be considered lost to follow-up.

Site is encouraged to perform the EMR review at the time of an in-office standard of care visit, if possible.

Print a copy of initial LATITUDE Clarity programming report to verify the time of the latest device transmission and print the applicable TSF for this visit. Data and source documentation requirements are summarized below in Table 10-6.

Data Collection	Retention of Original Source Documentation
ICM device transmission information	Study site
Information on arrhythmia diagnoses and related treatments since the LUXDx ICM implant	Study site
Reportable adverse events (as defined in Section 19.1) and protocol deviations, if applicable	Study Site

Table 10_6. 6.	and 12-Month	FMR Review	Source Documentation
1 abic 10-0. 0.	· and 12-month	THIN VENICA	Source Documentation

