11.1.3.2. Statistical Methods

The ICM system-related complication-free rate at 30 days post-implant will be calculated using Kaplan-Meier methodology. The 97.5% one-side lower pointwise confidence limit of

	Form/Template 92120219_Rev/Ver D
Confidential	LUX-Dx PERFORM Protocol, 92557593, Rev/Ver C
	Page 38 of 66

the ICM system-related complication-free rate will be calculated via log-log methodology and compared to the performance target of 94%. If the lower confidence limit exceeds 94% then the null hypothesis will be rejected.

The adjudication of the ICM system-related adverse events and complications will be conducted by independent physician reviewer(s).

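### A non-serious insertion-site event that the site confidently judges unrelated is not reportable, so the independent safety reviewer never sees it

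*Combined protocol and SAP*

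**What the plan says.** Section 19.1 sets what sites must report: "It is the responsibility of the investigator to assess and report to BSC any event which occurs in any of the following categories". The list takes in all serious adverse events without reference to cause, and likewise "Cardiac Related Adverse Events". The remaining routes for a non-serious adverse event are "Device Related Adverse Events" and the parallel category for study procedures. A fallback sentence adds events whose fit with a category is uncertain, and events that cannot be separated from the device or procedure.

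Follow-up collection uses the same list. Section 10.8, on the 6- and 12-month record reviews, says: "Reportable adverse events defined in Section 19.1 shall be collected".

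The anticipated implant effects in 18.2.2 include "Formation of hematomas or seromas", as well as infection, erosion, migration, local tissue reaction and tissue damage.

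On adjudication, 11.1.3.2 says: "The adjudication of the ICM system-related adverse events and complications will be conducted by independent physician reviewer(s". It sets no seriousness limit. Section 21.4 describes the independent review as covering serious adverse events reported by investigators. The available text does not define a complication.

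The acute test in 11.1.3.2 takes "The 97.5% one-side lower pointwise confidence limit of" the complication-free rate, by the log-log method, "compared to the performance target of 94"%. Section 11.1.4.2 does the same at 12 months against 93%.

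**The concern.** Both primary safety endpoints count events related to the ICM system. Independent adjudication is meant to take that causal judgement away from sites, which know the device in this open, single-arm study. For one class of event it cannot do so. A non-serious, non-cardiac event at the insertion site that the investigator confidently puts down to another cause meets no reporting category, so there is nothing for a reviewer to reclassify.

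These are the kinds of event that 18.2.2 anticipates from implantation, and many can fall short of the seriousness criteria in Table 19-1. Cardiac events, by contrast, are collected without a relationship filter.

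If such events can be endpoint complications, the error has one direction: an event that goes unreported can raise the complication-free rate and cannot lower it. That would push the chance of wrongly meeting a performance goal above the nominal one-sided 2.5%.

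**Working it through.** **Step 1. Follow one event through the plan.** Take a non-serious, non-cardiac event at the insertion site, treated with the device in place and confidently judged unrelated by the site.

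- Serious and cardiac categories of 19.1: not met.
- Device-related and procedure-related categories: not met, on the site's own judgement.
- Fallback in 19.1: not triggered, because the site is not in doubt.
- Table 19-2: defaults to possibly related when a link cannot be excluded or assessed. Section 19.3 applies the table to the reportable AE, and the site decides whether the default applies.
- Record review and subject contact (10.8): collect only events reportable under 19.1.
- Explant and disabling (10.9): not triggered.
- Monitoring (21.1): monitors read source documents, but a site that omitted this event has followed 19.1, so there may be no discrepancy to query.
- Adjudication (11.1.3.2 and 21.4): neither section reaches an unreported event.

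The event is not reliably recovered at any step.

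**Step 2. Find the pass/fail boundary.** Inputs: n = 227 (acute) and 226 (chronic), from 7.3; goals of 94% and 93%; one-sided 97.5% log-log limit. The text of 11.1.3.3 is not available, so the plan's sample sizes cannot be reproduced; many combinations of expected rate, power and attrition come close to them. They are taken as given.

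With d events and no censoring, S = 1 − d/n, SE = √[d/(n(n − d))] / |ln S|, and the lower limit is S^exp(1.96 × SE).

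| Endpoint | d of n | S | SE | Lower limit | Result |
|---|---|---|---|---|---|
| Acute, 94% | 6 of 227 | 97.36% | 0.408 | 94.21% | pass |
| Acute, 94% | 7 of 227 | 96.92% | 0.378 | 93.64% | fail |
| Chronic, 93% | 8 of 226 | 96.46% | 0.354 | 93.05% | pass |
| Chronic, 93% | 9 of 226 | 96.02% | 0.333 | 92.49% | fail |

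**Step 3. Illustrate what a loss would do.** Set the true rate exactly at the goal and assume that a share f of endpoint events is never reported. The chance of passing is P(X ≤ 6), X ~ Binomial(227, 0.06(1 − f)), for acute and P(X ≤ 8), X ~ Binomial(226, 0.07(1 − f)), for chronic.

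| Assumed f | Acute event probability | Acute pass | Chronic event probability | Chronic pass |
|---|---|---|---|---|
| 0% | 0.060 | 1.6% | 0.070 | 2.1% |
| 10% | 0.054 | 3.6% | 0.063 | 5.0% |
| 20% | 0.048 | 7.8% | 0.056 | 11.0% |
| 30% | 0.042 | 15.7% | 0.049 | 21.9% |

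The documents give no value for f. It can be thought of as the non-serious share of complications times the share of those that sites call unrelated: an assumed 50% × 20% gives 10%. If complications are serious events only, f = 0 by this route, because every serious event is reportable.

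**The case against.** The strongest reply has three parts.

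First, no positive relatedness call is required. The fallback in 19.1 takes in doubtful events, and Table 19-2 makes a confident exclusion hard to justify for a pocket hematoma or erosion: each is a known effect, at the body site where the device lies. Much of the feared misattribution would be a departure from Table 19-2 rather than a rule built into the plan. This stands, and it narrows the gap. It does not close it: Table 19-2 does not require every criterion for excluding a relationship to be met at once, and the site makes the call unseen.

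Second, the only visible description of endpoint review, in 21.4, concerns serious adverse events. On that reading nothing is lost. This also stands as a possible reading. But 11.1.3.2 names adverse events alongside complications with no seriousness limit, so the reading cannot be assumed.

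Third, the loss shares are hypothetical. That is correct; they show sensitivity and estimate nothing.

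A reader might go further and infer that reviewers can only remove events and never add them, and that both rates are therefore biased upward. The documents do not support this. Serious and cardiac events are reportable whatever the site thinks of their cause, so a serious event called unrelated can be added on review. Under 21.4 non-serious events would be neither added nor removed. Bias requires both that non-serious events count and that sites in fact misjudge some of them; neither is established.

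**Conclusion.** The concern holds as a narrow, conditional gap in event ascertainment. Non-serious, non-cardiac insertion-site events that a site confidently judges unrelated fall outside 19.1, and independent review cannot recover them. If such events can be complications, the resulting error can only favour meeting the goals, and a single event at the boundary can decide either endpoint.

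Its actual size is unknown. It is zero if complications are serious events only. Under an assumed 10% loss, the chance of passing at the goal moves from just under the nominal 2.5% to 3.6% (acute) and 5.0% (chronic). Those figures assume the planned 227 and 226 subjects, no censoring, and a true rate exactly at the goal. The change is worth making because it is cheap and removes a dependence on site attribution; existing safeguards already limit the risk.

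**What to change.** Add one category to 19.1: *Any adverse event at or around the ICM insertion site or pocket, from the implant or attempted implant to end of study, regardless of the investigator's relationship assessment.* Keep it to the insertion site or pocket. Tying it to the event types in 18.2.2 would bring in every infection or tissue injury anywhere in the body.

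State whether a non-serious event can be an ICM system-related complication. Reconcile 11.1.3.2 with 21.4 so that the existing independent reviewer decides the relationship of these insertion-site events for both safety endpoints. Widening 21.4 alone would not help, since it cannot reach events that were never reported.

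Cost: a protocol amendment with IRB/EC approval, a few extra adverse-event forms and reviews, and possibly a slightly lower observed complication-free rate.
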